6.1.2. Exclusion Criteria

Potential study patients may not be included in the study if any of the following apply during screening.

- [11] Have received treatment within 28 days of the initial dose of study drug with an investigational product or non-approved use of a drug or device (other than the study drug/device used in this study) for non-cancer indications or are concurrently enrolled in any other type of medical research judged not to be scientifically or medically compatible with this study.
- [12] Have serious preexisting medical conditions or concomitant disorders that, in the opinion of the investigator, would exclude the patient as a candidate for this study.

- [13] Have active central nervous system (CNS) or leptomeningeal metastasis (brain metastasis) at the time of study entry. Patients with a history of a CNS metastasis previously treated with curative intent (eg, stereotactic radiation or surgery) that have not progressed on follow-up imaging, have been asymptomatic for at least 28 days and are not receiving corticosteroids and/or anticonvulsants, are eligible. Patients with signs or symptoms of neurological compromise should have appropriate radiographic imaging performed before study entry to rule out brain metastasis.
- [14] Have current acute or chronic leukemia.
- [15] Have an active symptomatic fungal, bacterial, and/or known viral infection including human immunodeficiency virus (HIV) or viral (A, B, or C) hepatitis (screening is not required).
- [16] Have a second primary malignancy that, in the judgment of the investigator or Sponsor, may affect the interpretation of results.
- [17] Have Bazett's corrected QT interval (QTc) of >470 msec on screening electrocardiogram (ECG) in repeated measurements.
Note: Patients with permanent pacemakers may enter study if QTc is >470 msec if measured from a paced conduction and not an intrinsic (non-paced beat) conduction.
- [18] Have a serious cardiac condition, such as congestive heart failure; New York Heart Association Class III/IV heart disease; unstable angina pectoris; myocardial infarction within the last 3 months; valvulopathy that is severe, moderate, or deemed clinically significant; or arrhythmias that are symptomatic or require treatment (not including patients with rate-controlled atrial fibrillation).
- [19] Have a known allergy/history of hypersensitivity to any of the study drug components, or to monoclonal antibodies or other therapeutic proteins such as fresh frozen plasma, human serum albumin, cytokines, or interleukins.

6.2. Summary of Study Design

Study JNBA is a multicenter, nonrandomized, open label, dose escalation Phase 1 study of IV LY3164530 in patients with advanced and/or metastatic cancer. Eligible patients will receive LY3164530 as an infusion on Days 1 and 15 (Schedule 1) or on Days 1, 8, 15, and 22 (Schedule 2) of each cycle. A cycle will consist of 28 days and the schedules will enroll in parallel.

Dose escalation will be driven by a modified toxicity probability interval (mTPI) method. The RP2D and schedule will be determined once at least 10 patients, but no more than 20, are treated at a dose and schedule that is at or below the maximum tolerated dose (MTD). The actual sample size for Study JNBA is anticipated to be approximately 50 patients depending on the incidence of DLTs.

The planned duration of treatment is 2 cycles. Patients who are receiving benefit from study drug may continue to be treated with LY3164530 until 1 or more of the criteria for discontinuation have been fulfilled (Section 6.3.1).

6.2.1. Primary Endpoint Analysis, Study Completion, and End of Trial

The primary endpoint analysis will occur after the final patient enrolled has been evaluated for at least 1 cycle. Any patient enrolled that has completed at least 1 cycle of treatment or discontinued due to an AE (during Cycle 1), and completed the required post-treatment safety assessment, will be considered to have completed the study. However, additional cycles of therapy may continue as long as the patient is receiving benefit and no criteria for discontinuation have been met. All secondary/exploratory endpoint analyses will be updated at study completion.

Both the study completion and end of trial will be the date of the last visit or last scheduled procedure for the last patient.

6.3. Discontinuations

6.3.1. Discontinuation of Patients

The criteria for enrollment must be followed explicitly. If a patient who did not meet enrollment criteria and was inadvertently enrolled is identified, either by the Sponsor or investigator, a discussion must occur between the clinical research physician (CRP)/clinical research scientist (CRS) and the investigator to determine if the patient may continue in the study. The investigator must obtain documented approval from the Lilly CRP/CRS to allow the inadvertently enrolled patient to continue in the study with or without treatment with study drug.

In addition, patients will be discontinued from the study drug and from the study in the following circumstances:

- Enrollment in any other clinical trial involving an investigational product or enrollment in any other type of medical research judged not to be scientifically or medically compatible with this study.

- Investigator/Physician Decision
 - the investigator/physician decides that the patient should be discontinued from the study or study drug
- Patient Decision
 - the patient requests to be discontinued from the study or study drug
- Sponsor Decision
 - Lilly stops the study or stops the patient's participation in the study for medical, safety, regulatory, or other reasons consistent with applicable laws, regulations, and GCP
- The patient has radiographic progressive disease or significant symptomatic disease deterioration characterized as progression of disease, in the opinion of investigator, in the absence of radiographic evidence of progressive disease.
- The patient experiences unacceptable toxicity.
- The patient is noncompliant with study procedures and/or treatment (Section 7.6).
- A dose cannot be administered within 28 days of the prior dose due to an AE (except as noted in Section 7.2.5.1).

6.3.2. Discontinuation of Study Sites

Study site participation may be discontinued if Lilly, the investigator, or the ethical review board (ERB) of the study site judges it necessary for any scientific, medical, safety, regulatory, ethical, or other reasons consistent with applicable laws, regulations, and GCP.

6.3.3. Discontinuation of the Study

The study will be discontinued if Lilly, while considering the rights, safety, and well-being of the patient(s), judges it necessary for any scientific, medical, safety, regulatory, ethical, or other reasons consistent with applicable laws, regulations, and GCP.

7. Treatment

7.1. Materials and Supplies

LY3164530 is supplied for clinical trial use as a lyophilized powder in a glass vial. The vial is manufactured to deliver 75 mg of LY3164530. LY3164530 will be supplied to the investigative sites by Lilly. Detailed instructions for the reconstitution of the study drug and the preparation of the different dilutions will be provided separately by the Sponsor.

LY3164530 should be stored refrigerated at 2 to 8°C.

7.2. Study Drug Administration

The investigator or designee is responsible for:

- explaining the correct use of the investigational agent and planned duration of each individual's treatment to the site personnel or patient
- verifying that instructions are followed properly
- maintaining accurate records of study drug dispensation, destruction, and collection
- returning or destroying all unused medication to Lilly or its designee at the end of the study.

Patients will be instructed to contact the investigator as soon as possible if they have a complaint or problem with the study drug(s) so that the situation can be assessed.

7.2.1. Dosing Schedule

For doses ≤ 1000 mg, LY3164530 will be administered intravenously over approximately 60 minutes. The Sponsor may instruct sites to extend the infusion time for up to 3 hours for doses >1000 mg.

LY3164530 will be administered on Days 1 and 15 every 28 days (Schedule 1) or on Days 1, 8, 15, and 22 every 28 days (Schedule 2). The assigned dose, schedule, and duration of infusion of LY3164530 will be provided by the Sponsor on a patient registration form. A patient will be assigned to either Schedule 1 or Schedule 2 and will be maintained on that schedule for the duration of therapy. Subsequent doses and/or infusion times should be adjusted as described in Section [7.2.5](#).

7.2.2. Dose Escalation

7.2.2.1. Dose-Limiting Toxicity Determination

Dose-limiting toxicity is defined as an AE during Cycle 1 that is considered by the investigator to be at least possibly related to LY3164530 and fulfills any one of the following criterion using the National Cancer Institute (NCI) Common Terminology Criteria for Adverse Events (CTCAE) v 4.03:

- \geq Grade 3 non-hematological toxicity. Exceptions will be made for:

- nausea, vomiting, diarrhea, and constipation that can be controlled with treatment. Grade 3 and Grade 4 nausea, vomiting, or diarrhea should be considered DLTs if persisting more than 48 hours despite supportive intervention.
 - Grade 3 rash that resolves with treatment to \leq Grade 1 within 14 days
 - Grade 3 or 4 asymptomatic electrolyte abnormalities that respond to standard treatment
 - Grade 3 elevations of ALT and/or AST lasting fewer than 8 days, without evidence of other hepatic injury, in the setting of preexisting hepatic metastasis and baseline elevation of these values, may not be considered a DLT if agreed by the study investigator and Lilly CRP/CRS.
- Grade 4 neutropenia or leukopenia, of >7 days duration.
 - Grade 4 thrombocytopenia of any duration.
 - Grade 3 thrombocytopenia with bleeding.
 - Any febrile neutropenia.
 - Any other significant toxicity deemed by the primary investigator and Lilly clinical research personnel to be dose limiting (eg, any toxicity that is possibly related to the study drug that requires the withdrawal of the patient from the study during Cycle 1).

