7.6.1. Evaluable Patients

Patients who withdraw from the study before receiving study drug will be replaced and will not be included in the safety or efficacy assessments. Safety analyses will be conducted on all patients who have been exposed to study drug, regardless of whether they are deemed evaluable for the assessment of a dose level.

Any patient who is discontinued from the study before completing 1 cycle of LY3164530 treatment will be deemed non-evaluable for assessment of a dose level, unless they experience a DLT prior to withdrawal. However, patients who receive all doses of LY3164530, but discontinue from study drug before the end of Cycle 1, will be considered evaluable for the assessment of a dose level, provided it can be documented whether the patient experienced a DLT during Cycle 1.

If the patient is noncompliant during Cycle 1 due to reasons other than drug-related toxicity, he or she will be considered non-evaluable and may be replaced.

Patients that require a dose reduction or omission during Cycle 1 or have a dosing delay of more than 3 days for reasons other than a study drug-related AE may be deemed non-evaluable for DLT assessment.

Nonevaluable patients may be replaced to ensure that enough patients complete 1 cycle of therapy at each dose level, unless accrual to that cohort has stopped due to a DLT.

Patients who are not evaluable for PK, but who complete 1 cycle of therapy, may be replaced upon consultation with the investigator(s) and the Lilly CRP or CRS to ensure adequate PK data, unless accrual to that cohort has stopped due to a DLT.

8. Safety, Pharmacokinetic, Pharmacodynamic, and Efficacy Data Collection

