6.3. Handling of Dropouts or Missing Data

Missing data will not be imputed.

Patients who withdraw from the study before receiving study drug will be replaced.

In the following situation, patients will be considered non-evaluable and may be replaced to ensure that enough patients complete 1 cycle of therapy at each dose level, unless accrual to that cohort has stopped due to a DLT:

1. Any patient who is discontinued from the study before completing 1 cycle of LY3164530 treatment unless they experience a DLT prior to withdrawal
2. Patients who are not evaluable for PK

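### A qualifying event after early withdrawal but still within Cycle 1 is a DLT under the definition, yet the evaluability rule can remove that patient from the mTPI grid

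*Protocol*

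**What the plan says.** **DLT definition.** Protocol 7.2.2.1 reads "Dose-limiting toxicity is defined as an AE during Cycle 1 that is considered by the investigator to be at least possibly related to LY3164530" and then lists graded criteria; SAP 6.13 uses the same Cycle 1 window. Neither requires the patient to be on drug when the event occurs. The last criterion is a judgement: "Any other significant toxicity deemed by the primary investigator and Lilly clinical research personnel to be dose limiting". Its example is "any toxicity that is possibly related to the study drug that requires the withdrawal of the patient from the study during Cycle 1".

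**Evaluability.** Under protocol 7.6.1, a patient "discontinued from the study before completing 1 cycle of LY3164530 treatment will be deemed non-evaluable" for the dose level, "unless they experience a DLT prior to withdrawal". The next sentence makes an exception for patients who received every dose but stopped drug before the end of Cycle 1. Such a patient "will be considered evaluable for the assessment of a dose level, provided it can be documented whether the patient experienced a DLT during Cycle 1". Non-evaluable patients may be replaced. SAP 6.3 lists as non-evaluable "Any patient who is discontinued from the study before completing 1 cycle of LY3164530 treatment unless they experience a DLT prior to withdrawal" and does not repeat the all-doses exception.

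**Collection of events.** Protocol 8.1.2.2.3 and Table JNBA.5 require all AEs to be reported through a follow-up assessment 28 ± 5 days after the last dose.

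**The concern.** The definition asks when the event happened relative to Cycle 1. The evaluability rule asks when it happened relative to withdrawal. For a patient who stops early, the two can give opposite answers about one event.

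The conflict can arise with this drug. Protocol 7.2.4.2 reports that skin reactions were dose limiting at 1250 mg on Schedule 1, and Grade 3 rash becomes a DLT only if it fails to resolve within a set period. Some DLTs are therefore confirmed well after onset.

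The primary objective is a recommended Phase 2 dose, and escalation reads the counts of patients and DLTs from Figure JNBA.1. A patient dropped as non-evaluable leaves both counts. If the replacement has no DLT, the reading can only stay the same or become more permissive.

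**Working it through.** **1. The rules applied to one patient.** As an illustration, Grade 3 related rash starts on Day 8 and the patient withdraws on Day 12 with a Cycle 1 dose still to come. Protocol 7.2.2.1 exempts rash that resolves to Grade 1 or less within 14 days, so status is open until Day 8 + 14 = Day 22. SAP 6.13 words this exemption differently (Grade 2 or less within 8 days), which gives Day 16. Under either wording the DLT is unconfirmed at withdrawal. An event that first appears on Day 20 is a plainer case: it is inside Cycle 1 and after withdrawal.

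**2. Who is exposed.** Schedule 1 doses on Days 1 and 15, so the gap concerns patients who stop after Day 1 only. A patient who stops after the second infusion has had all Cycle 1 doses and is covered by the 7.6.1 exception. Schedule 2 doses on Days 1, 8, 15 and 22, so the gap concerns patients who stop after one, two or three infusions.

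**3. Are the events collected?** If the last dose was on Day 1, the follow-up assessment falls between Day 1 + 28 − 5 = Day 24 and Day 1 + 28 + 5 = Day 34. If it was on Day 8, the earliest is Day 8 + 23 = Day 31. Collection of all AEs therefore covers Cycle 1, except possibly Days 25 to 28 for a patient dosed only once, or where follow-up is shortened for a new anticancer therapy. After that visit, 8.1.2.2.3 still asks for events the investigator considers drug related, and a DLT must be at least possibly related.

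**4. Reproducing Figure JNBA.1.** From the protocol: target 0.30 and equivalence interval (0.287, 0.301), so ε₁ = 0.013 and ε₂ = 0.001. Assumed, because not stated: a Beta(1,1) prior, and DU when P(p > 0.30) > 0.95. With x DLTs in n patients the posterior is Beta(1 + x, 1 + n − x). The unit probability mass is the posterior probability of an interval divided by its length (0.287, 0.014 and 0.699), and the largest decides. All 125 cells in rows 0 to 6 match the protocol grid. A cutoff of 0.90 gives 8 mismatches. Rows 7 and above were not compared because the extracted table is broken there.

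**5. Effect of one patient.**

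| DLTs/patients | Mass E | Mass S | Mass D | Decision |
|---|---|---|---|---|
| 1/3 | 1.134 | 1.758 | 0.930 | S |
| 0/3 | 2.584 | 1.408 | 0.342 | E |
| 2/6 | 1.128 | 2.254 | 0.922 | S |
| 1/6 | 2.238 | 2.166 | 0.468 | E |

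For 0/3, for example: E = (1 − 0.713⁴)/0.287 = 2.584 and S = (0.713⁴ − 0.699⁴)/0.014 = 1.408.

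These changes need a replacement without a DLT. If the patient is dropped and not replaced, 2/6 becomes 1/5, still S, and 1/3 becomes 0/2, below the three-patient minimum. Some readings do not move at all: 3/6 and 2/6 are both S.

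**6. Sensitivity, with an assumed share.** Let f be the share of DLT patients dropped and replaced. The documents give no value. The apparent rate is q = p(1 − f)/(1 − pf), and the chance of escalating at 0/3, or at 1/3 followed by 1/6, is (1 − q)³ + 3q(1 − q)⁵.

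| True p | f = 0 | f = 0.02 | f = 0.05 | f = 0.10 |
|---|---|---|---|---|
| 0.30 | 49.4% | 50.3% | 51.6% | 53.9% |
| 0.40 | 30.9% | 31.7% | 33.0% | 35.1% |

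**The case against.** **Toxicity that forces withdrawal is already counted.** A reader might infer that toxicity-driven withdrawals as a class leave the grid and are replaced. The documents do not support that. The last DLT criterion names related toxicity that requires Cycle 1 withdrawal as its example. Such toxicity precedes the withdrawal, so once deemed dose limiting the patient stays in both counts.

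**Leaving the study may come later than stopping drug.** The rule concerns patients discontinued from the study, and 8.1.2.2.3 places that after the follow-up assessment. On that reading, most events through Day 28 precede withdrawal. Protocol 6.2.1 also treats a patient who discontinues for an AE in Cycle 1 and completes the safety assessment as having completed the study. This is the strongest objection, and it would close most of the gap if the text were consistent. It is not. Protocol 6.3.1 ends study drug and study together under one list of reasons. In 7.6.1, the all-doses exception for patients who stop drug would hardly be needed unless stopping drug triggered the rule.

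**The SAP may already cover patients who received all doses.** SAP 6.13.2 says a cycle is completed when all its planned treatment was received, which could stand in for the missing exception. It sits in the exposure section and lacks the condition that DLT status be documented, so SAP 6.3 should still state the exception.

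**Lower-grade toxicity is left to judgement.** The reduction, omission and delay rule reaches only cases "for reasons other than a study drug-related AE may be deemed non-evaluable for DLT assessment", whereas the withdrawal rule has no such limit. A reader might infer that every withdrawal for a related AE should count as a DLT. But joint judgement on toxicity below the graded criteria is a legitimate design choice. These patients remain in the safety analyses, safety data are the primary criterion for escalation, and a more conservative decision is always allowed. This supports showing the cases, not a new escalation rule.

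**Conclusion.** The conflict is real but narrow. It affects a patient who stops before receiving all Cycle 1 doses and whose related qualifying event appears, or is confirmed, after stopping and by Day 28. It depends on reading withdrawal as stopping study drug, which the documents neither adopt nor exclude.

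No overall bias can be stated. A reader might infer a sizeable upward push on the selected dose by assuming that 5% or 10% of patients are lost this way, but nothing in the documents supports those rates. Small assumed shares of DLT patients move the escalation probability by only about one to four and a half percentage points (f from 0.02 to 0.10). At the level of a single decision, one dropped and replaced patient can turn S into E at 1/3 or 2/6. The direction is always towards escalation. It is worth correcting because the rule feeds the primary dose decision and the correction is small.

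**What to change.** Reconcile protocol 7.2.2.1 and 7.6.1 with SAP 6.3 and 6.13:

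- In 7.6.1 and SAP 6.3, replace "unless they experience a DLT prior to withdrawal" with wording that keeps a patient evaluable if a DLT as defined in 7.2.2.1 occurs at any time in Cycle 1 (Days 1 to 28), including after study drug is stopped.
- Carry the all-doses exception of 7.6.1, with its documentation condition, into SAP 6.3.
- List Cycle 1 withdrawals attributed to a related AE not deemed a DLT by dose level, beside the grid reading, as a sensitivity display. This adds no escalation rule.

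The cost is about one sentence for each change and one listing. The AEs are already collected, apart from the possible Day 25 to 28 gap noted above. Escalation will be slightly more cautious when such a case occurs.

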7.2.2.2. DLT-Equivalent Toxicities

A DLT-equivalent toxicity is defined as an AE occurring in Cycle 2 and beyond that would have met the criteria for a DLT if it had occurred during Cycle 1. For individual patients experiencing a DLT-equivalent toxicity, dose adjustments will be made as outlined in Section 7.2.5.

At each interim analysis (as defined in Section 10.10), the rate of DLT-equivalent toxicities will be assessed. If the rate of DLT-equivalent toxicities is unacceptable (eg, a DLT-equivalent toxicity is observed in $>33\%$ patients at a given dose level), then a safety analysis will be triggered and the data will be reviewed by study investigators and the Lilly CRP/CRS. If the findings indicate that a dose level does not have an acceptable safety profile for chronic (Cycle 2 or later) administration, then a lower dose level will be chosen for further investigation. This decision will be documented in writing.

7.2.2.3. Dose Escalation Method

Dose escalation will be driven by a mTPI method (Ji and Wang 2013) (Attachment 7). A 3+3 design is commonly used in Phase 1 trials due to its simple, intuitive, and pre-specified escalation rules. However, the 3+3 method has been criticized for being conservative because the method is dictated by the observed DLT rate without acknowledging the variability arising from small cohort size.

Like the 3+3 design, the mTPI method incorporates pre-specified escalation rules. In contrast, the mTPI method is based on quantitative models that incorporate uncertainty into the decision

rules, thereby allowing more aggressive dose escalation. In the mTPI method, the number of patients in each cohort is not fixed, but a minimum of 3 patients are required for this study at each dose (unless the rule in the table indicates to deescalate the dose due to unacceptable toxicity [DU]). If 3 to 6 patients are enrolled in a cohort, the escalation rule parallels a traditional 3+3 design. However, the stay/deescalation rule of the mTPI is more aggressive than the 3+3 design. For instance, with 2 to 3 DLTs per 6 patients enrolled, the mTPI would recommend staying at the current dose, whereas the 3+3 design would recommend deescalation. [Figure JNBA.1](#) provides the mTPI escalation rules for any cohort size up to 20 patients.

In [Figure JNBA.1](#), the number of patients dosed at a given dose level are shown in the columns (x-axis), while the number of DLTs experienced are shown in the rows (y-axis). The rules in this figure will be used for each dose level evaluated; the patient numbers and DLTs do not carry over from cohort to cohort. By locating the intersection of the number of patients dosed and the number of DLTs, 1 of 4 pre-defined rules is used:

- E: Escalate the dose
- S: Stay at the same dose
- D: Deescalate the dose
- DU: Deescalate the dose due to unacceptable toxicity. The dose cannot be re-escalated to this dose level at a future point in the escalation.

If agreed upon by the investigators and Sponsor (for instance, if PK/PD data suggest that increasing the dose further is not expected to yield additional benefit), a more conservative rule may be applied. For instance, if the rule indicates “E” to escalate, the dose may remain at the current dose level or be deescalated to a lower level.

As shown in [Figure JNBA.1](#), if 1 of 3 patients experiences a DLT, the decision (located in column 3 row 1) is “S”, stay at the same dose. Therefore, the next patient must be treated at the same dose level. If 1 of 6 patients experience a DLT, the decision (located at column 6 row 1) is “E”, escalate the dose. However, if 2 of 3 patients experience a DLT the decision is “D” and the dose must be deescalated.

In the mTPI, the cohort size is not fixed. However, each cohort in this study will contain a minimum of 3 patients, unless the escalation rules dictate that the dose should be deescalated due to unacceptable toxicity (“DU”). Doses can be escalated, deescalated, and re-escalated following the rules in [Figure JNBA.1](#). If the dose decision was “DU,” the dose cannot be re-escalated to that level.

This study is designed to identify a dose level with a dose-limiting target toxicity rate of 30%. In reality, the exact target toxicity rate is almost never achieved for a dose. To this end, instead of using a single target rate, the mTPI method considers an equivalence interval (EI) around the target toxicity rate. For this study, the EI is calibrated to be (28.7%, 30.1%), resulting in the rules in [Figure JNBA.1](#). If the observed toxicity rate exceeds 40% and the model is still recommending “S”, the Sponsor, in discussion with the investigators, may choose to deescalate. Deescalation may not be required for toxicities confounded by patient comorbidities or other clinical factors that make direct attribution to study drug difficult to determine, particularly if

they are deemed non-serious (eg, fatigue, anorexia), reversible, or inconsistent with the known toxicities of MET or EGFR inhibitors by study investigators and the Lilly CRP/CRS.

		Number of patients treated at current dose																			
		1	2	3	4	5	6	7	8	9	10	11	12	13	14	15	16	17	18	19	20
Number of DLTs	0	E	E	E	E	E	E	E	E	E	E	E	E	E	E	E	E	E	E	E	E
	1	D	S	S	S	S	E	E	E	E	E	E	E	E	E	E	E	E	E	E	E
	2		DU	D	S	S	S	S	S	S	S	E	E	E	E	E	E	E	E	E	E
	3			DU	DU	D	S	S	S	S	S	S	S	S	S	S	E	E	E	E	E
	4				DU	DU	DU	D	D	S	S	S	S	S	S	S	S	S	S	S	S
	5					DU	DU	DU	DU	DU	D	S	S	S	S	S	S	S	S	S	S
	6						DU	DU	DU	DU	DU	DU	D	S	S	S	S	S	S	S	S
	7							DU	D	D	S	S	S	S	S						
	8								DU	D	S	S									
	9									DU	D										
	10										DU										
	11											DU									
	12												DU								
	13													DU							
	14														DU						
	15															DU	DU	DU	DU	DU	DU
	16																DU	DU	DU	DU	DU
	17																	DU	DU	DU	DU
	18																		DU	DU	DU
	19																			DU	DU
	20																				DU

E = Escalate to the next higher dose
 S = Stay at the current dose
 D = De-escalate to the next lower dose
 U = The current dose is unacceptably toxic
 MTD = 30%
 Equivalence Interval = (28.7%, 30.1%)

Figure JNBA.1. Dose-finding spreadsheet of the modified toxicity probability interval method showing number of patients treated at a given dose vs. number of DLTs observed at that dose .

The beginning dose level for Schedule 1 was 300 mg. The starting dose level for Schedule 2 will be 500 mg. The dose will be escalated by a maximum increment of 100%. If the beginning dose level is determined to be unacceptably toxic, a -1 dose level may be explored.

The exact increment will be determined by the investigators and Lilly CRP/CRS, and may be less than the maximum increment allowed in the protocol. Safety data will be the primary criteria for both the decision to dose-escalate and for selecting the dose to be administered in the next cohort. In addition, if available at the time of the dose escalation decision, PK (maximum serum concentration [C_{max}], area under the serum concentration-time curve [AUC], and CL) and/or PD results will be used as secondary/supporting data for dose escalation. No dose escalation can occur without prior discussion and agreement between the investigator and the Lilly CRP or CRS; the decision will be documented in writing. Inpatient dose escalations are not permitted.

Although an example escalation table is shown in [Table JNBA.3](#), alternate doses may be selected.

Table JNBA.3. Sample Dose Escalation Schema

Dose Level (Cohort)	Schedule 1 Dose	Schedule 2 Dose
-1	100 mg	400 mg
1	300 mg	500 mg
2	600 mg	600 mg
3	1000 mg	700 mg
4	1250 mg	

In Cohort 1 for Schedule 1 only, the first patient is required to complete a full cycle (28 days) before subsequent patients can be dosed. Subsequent patients in Cohort 1 can be dosed concurrently. Beginning with Cohort 2 for Schedule 1 and for all cohorts with Schedule 2, patients within a cohort can be dosed concurrently.

The decision to stop dose escalation will be primarily driven by the appearance of DLTs and the rules in [Figure JNBA.1](#). However, if PK/PD data suggest that increasing the dose further is not expected to yield additional benefit, escalation may cease.

